- Program safety. Recognition that certain programs are not appropriate for certain situations. E.g. Program 4 is a directional microphone program and thus is not appropriate for driving a car due to compromised awareness of sound behind you such as sirens.

Part Two: Clinical Testing Protocol: Laboratory Evaluation of Validity of MDHearing Self-Fitting Method

- Subjects:
 - 75 subjects with mild to moderate sensorineural hearing loss.
 - Subjects will not be allowed to participate if they have any signs of middle or outer ear infection or abnormality.
 - All subjects will undergo a hearing evaluation to ensure they do not have any of the following conditions:
 - Visible congenital or traumatic deformity of the ear.
 - History of active drainage from the ear in the previous 90 days.
 - History of sudden or rapidly progressive hearing loss within the previous 90 days.
 - Acute or chronic dizziness.
 - Unilateral hearing loss of sudden or recent onset within the previous 90 days.
 - Audiometric air-bone gap equal to or greater than 15 decibels at 500 Hz, 1,000 Hz, and 2,000 Hz.
 - Visible evidence of significant cerumen accumulation or a foreign body in the ear canal.
 - Pain or discomfort in the ear.
 - At least one air conduction threshold must be above 25dB. All air conduction thresholds must be below 60db.
 - Subjects will be at least 18 years old. There are no other limits on subject age.
- Protocol and ANSI specs
 - Subjects take the personalization profile on an iPad tablet.
 - Subjects then listen to the same recorded speech passage at their Most Comfortable Listening level 3 times and adjust the aids for comfort (volume, bass, treble, and mid) while the passage is playing. Subjects do not have to make changes if they are content with the sound quality.
 - After each passage, Real Ear measurements will be taken. Gain results at 500, 1000, 2000, and 4000Hz for a 60dB input will be recorded.

• The differences between gain for each frequency will be evaluated per subject. See table below for example:

Subject		500Hz	1000Hz	2000Hz	4000Hz	Total gain
1						deviation
	Passage 1	15dB	18dB	20dB	23dB	
	Passage 2	17dB	19dB	22dB	22dB	
	Passage 3	14dB	18dB	19dB	24dB	
	Average	2.5	1	2.5	1.5	1.9dB
	deviations					

Part Three: Comparative Clinical_Testing Protocol: Clinical Validation of MDHearing Self-Fitting Method

- Subjects
 - 75 subjects with mild to moderate sensorineual hearing loss.

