 - Subjects must have and be able to use a smartphone that is compatible with the MDHearing app.
 - Subjects will not be allowed to participate if they have any signs of middle or outer ear infection or abnormality.
 - All subjects will undergo a hearing evaluation to ensure they do not have any of the following conditions:
 - Visible congenital or traumatic deformity of the ear.
 - History of active drainage from the ear in the previous 90 days.
 - History of sudden or rapidly progressive hearing loss within the previous 90 days.
 - Acute or chronic dizziness.
 - Unilateral hearing loss of sudden or recent onset within the previous 90 days.
 - Audiometric air-bone gap equal to or greater than 15 decibels at 500 Hz, 1,000 Hz, and 2,000 Hz.
 - Visible evidence of significant cerumen accumulation or a foreign body in the ear canal.
 - Pain or discomfort in the ear.
 - At least one air conduction threshold must be greater than 25dB. All air conduction thresholds must be less than 60db.
 - Subjects will be at least 18 years old. There are no other limits on subject age.
- First visit
 - A hearing test is performed on all subjects.
 - Subjects complete the Abbreviated Profile of Hearing Aid Benefit (APHAB) and Speech, Spatial, and Qualities of Hearing Scale (SSQ-12).
 - Subjects complete the Quick SIN. (Speech in Noise test)

- All subjects use the MDHearing CORE with the tubing and ComfortTIP that is appropriate for their hearing loss. The tubing and ComfortTIP selection is audiologist fit to half the participants. The other half of the participants chose their own tubing and ComfortTIP. The tubing options are thin tubing with open ComfortTIP or thin tubing with closed ComfortTIP.
- The subjects are split into two groups.
 - The groups are controlled for demographic such as age, gender, length of hearing loss, previous hearing aid use, length of hearing aid use, comfort with technology and level of sensorineural hearing loss.
- Half of the subjects take the MDHearing personalization profile and are fit using NAL NL
 2 fitting software embedded in the MDHearing app. (Self-fit group)
- Half of the subjects are fit using hearing aid fitting software with the NAL NL 2 fitting method. (Audiologist fit group)
- The subjects that are self-fit have access to changing their volume control, programs, bass, treble, and mid pitched settings, noise reduction, and microphone direction using the MDHearing app.

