2.3. Secondary Endpoints and Other Effectiveness Measures

The Clinical study will have the following secondary endpoints: speech-in-noise (objective) aided benefit, self-fit user satisfaction, appropriateness (or validity) and reliability of self-fitting method, and robustness of the personalization process to estimate hearing sensitivity for self-fitting using the MDHearing app.

Objective benefit will be considered acceptable if self-fit users have significantly non-inferior benefit scores for speech in noise performance on the QuickSIN compared with the professionally-fit group.

Quick SIN will be performed at two presentation levels: 70 dB HL and Most Comfortable Loudness Level (MCL).

Self-fit participants' satisfaction with sound quality, cost of devices, and ease of device use is evaluated by questionnaire. Sound quality and device cost is considered satisfactory if a majority of respondents are "satisfied" or "very satisfied" according to questionnaire responses; ease of use is considered satisfactory if a majority of questionnaire responses indicate that the hearing aids were easy to operate or that they were able to operate the devices.

The reliability and validity endpoints for in-lab hearing aid performance testing are probe-microphone measures of hearing aid output in the ear canal. The self-fitting method is considered to be reliable if average mean absolute differences (MAD) in the real ear aided response (REAR) measured from 500-4000 Hz after each experimental trial (or run) of user-based self-fitting is 5 dB or less with significance testing. The REAR of professionally-selected hearing aid settings achieved as part of the initial fitting of the hearing aids for professional-fit group participants will be evaluated for proximity to NAL-NL2 prescriptive targets at the respective test frequencies, and amplification will be deemed adequate for the intended user population (adults with mild to moderate hearing loss) if a subjectively close approximation to targets, on average, is achieved.

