Participants' hearing levels in each ear from 500-6000 Hz as measured in a quiet room using the MDHearing app installed on a smartphone or tablet (i.e., the personal profile) is compared to their "gold standard" audiometric pure tone thresholds obtained by a clinician using an audiometer in a double-walled sound-treated booth to evaluate the robustness of the personalization process for estimating hearing sensitivity using the MDHearing app; this endpoint will be met if the average difference between personal profile and audiogram is within 10 dB, with a 95% confidence interval.

3. Software

All analyses will be performed using an established statistical computing software (MATLAB, R, JMP).

4. Data Collection

Due to the COVID-19 pandemic, it is understood some subjects may not be able to attend their appointments as scheduled. In that case, subjects will be scheduled as soon as they are able to safely attend appointments. Missing data will be noted as such.

5. Data Use

Human factors endpoints will be used to determine if the current user manual and/or MDHearing app need to be adjusted to ensure user success and safe operation of the devices.

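### The accuracy rule for the in-app hearing profile rests on an undefined average difference; read as a signed mean, opposite errors cancel and an inaccurate profile can pass the 10 dB limit

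*SAP*

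**What the plan says.** SAP section 2.3 makes the accuracy of the in-app hearing test a secondary endpoint. The data are "Participants' hearing levels in each ear from 500-6000 Hz as measured in a quiet room using the MDHearing app", set against clinician-measured thresholds from a sound booth. The stated purpose is "to evaluate the robustness of the personalization process for estimating hearing sensitivity using the MDHearing app". The pass rule is: "this endpoint will be met if the average difference between personal profile and audiogram is within 10 dB, with a 95% confidence interval".

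Earlier in the same section, the reliability endpoint for self-fitting is written with an explicitly absolute metric, "average mean absolute differences (MAD"), and a 5 dB limit.

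The protocol plans no comparison of profile with audiogram. In Part Two all 75 subjects take the profile. In Part Three, "Half of the subjects take the MDHearing personalization profile". Part Two also has a worked table of gain differences, introduced by "The differences between gain for each frequency will be evaluated per subject".

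**The concern.** The rule leaves four things open: signed or absolute difference; how ears, frequencies and subjects are combined; whether the whole confidence interval or only the point estimate must be within 10 dB; and which subjects are analysed.

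The first matters most. In a signed mean, a user whose hearing loss is overestimated offsets one whose loss is underestimated. The confidence interval does not prevent this. It describes the precision of the average bias and narrows as the sample grows, whatever the size of the individual errors. Neither document limits individual profile error in any other way.

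The profile is the hearing estimate from which the self-fit starting gain is set, and this is the only endpoint that tests it. Users can adjust settings later, and APHAB, SSQ12 and QuickSIN may reveal poor fits, but none of these measures profile accuracy. The sponsor could therefore call the profile robust when it is wrong for many individuals, and the same data could pass or fail depending on which reading the analyst takes.

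**Working it through.** The plan gives no SD, power or sample size for this endpoint, so there is no figure of its own to reproduce.

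**Inputs**
- Limit 10 dB and 95% confidence: SAP 2.3.
- n = 75 (Part Two) or 37 (about half of the 75 in Part Three). Which sample applies is not stated, so both are shown.
- Assumed: errors normal with mean 0 and SD 8 to 20 dB, one value per subject, whole interval required inside ±10 dB.

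**Step 1. Cancellation without a distributional assumption.** Let half of 38 subjects be off by +20 dB and half by -20 dB. The signed mean is 0.0 dB, with 95% CI -6.7 to +6.7 dB, so the rule is met. Every individual error is 20 dB, and so is the mean absolute difference.

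**Step 2. Formulas.**
- Mean absolute error = SD × √(2/π) = 0.798 × SD.
- Share of errors beyond 10 dB = 2 × [1 - Φ(10/SD)].
- Average half-width of the CI ≈ t(0.975, n-1) × SD/√n. At SD 15 dB: 1.993 × 15/√75 = 3.45 dB, and 2.028 × 15/√37 = 5.00 dB.

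**Step 3. Simulated pass rates.** Signed rule: the t interval of the mean difference lies inside ±10 dB. Absolute rule: the upper 95% limit of the mean absolute difference is no more than 10 dB.

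| SD (dB) | Mean absolute error (dB) | Errors beyond 10 dB | Signed, n=37 | Signed, n=75 | Absolute, n=37 | Absolute, n=75 |
|---|---|---|---|---|---|---|
| 8 | 6.4 | 21% | 100% | 100% | 98% | >99.9% |
| 10 | 8.0 | 32% | >99.9% | 100% | 52% | 79% |
| 15 | 12.0 | 50% | 95% | >99.9% | 0.2% | <0.1% |
| 20 | 16.0 | 62% | 68% | 98% | 0% | 0% |

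**Step 4. Several thresholds per subject.** With an assumed 12 values per subject and within-person correlation 0.1 to 1.0, the signed rule at SD 15 dB passes 95% to 100% of the time at n=37 and over 99.9% at n=75. The absolute rule passes at most 0.2% in every case. One value per subject is equivalent to perfect correlation, the least favourable case for the signed rule.

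**Step 5. A profile that ignores the listener.** Eligibility requires all thresholds below 60 dB. Suppose thresholds were spread evenly over 10 to 60 dB (an assumption) and the app returned 35 dB for everyone. Errors are then uniform over ±25 dB, and 1 - 10/25 = 60% exceed 10 dB. The signed rule passes 97% of the time at n=37 and over 99.9% at n=75; the absolute rule passes under 0.01%.

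**Step 6. What the documents mean by a difference.** In the Part Two table, the 500 Hz gains are 15, 17 and 14 dB. The successive absolute differences 2 and 3 average 2.5, as printed. The other columns give 1, 2.5 and 1.5; overall (2.5 + 1 + 2.5 + 1.5)/4 = 1.875, printed as 1.9 dB. Signed differences would give -0.5, 0, -0.5 and 0.5, overall -0.125 dB. The text there says only differences, yet the arithmetic is absolute.

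**The case against.** The strongest reply is that this is loose wording and the sponsor meant absolute differences all along. Its only worked example of a difference (Step 6) is absolute, although the text does not say so. This stands as a reason for medium confidence about intent. It does not settle the rule: the reliability endpoint in the same section names an absolute metric and this one does not, so the plain reading here is signed.

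The phrase "within 10 dB, with a 95% confidence interval" might also have been meant as 95% of individual differences lying within 10 dB. That would limit individual error, to an SD of about 5.1 dB at zero bias (10/1.96), but the text does not say it.

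The assumed SDs of 15 and 20 dB can be called severe. With thresholds even over 0 to 60 dB, a constant 30 dB profile would have an SD of 60/√12 = 17.3 dB, so an SD of 20 dB is worse than ignoring the user. That is fair, and at 8 dB or less with little bias the choice of metric hardly matters. But an accuracy endpoint should be able to fail a profile that carries no individual information, and the signed rule usually would not.

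The protocol also compares real-ear gain with hearing loss in both groups at the second visit. That looks at a consequence of the profile; it is a group comparison and does not measure profile accuracy.

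Finally, the SAP describes recruitment in the past tense, so a tighter rule could look post hoc. This bears on how the change is documented; the rule still needs a definition.

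**Conclusion.** The concern holds. As written, the endpoint can be declared met when about half of the in-app thresholds are wrong by more than 10 dB: about 95% of the time with 37 subjects and almost always with 75, at zero bias and an SD of 15 dB. The cancellation itself needs no distributional assumption. How often it would mislead depends on an error SD that the documents do not give, and with a truly accurate app both readings pass. The absolute reading cannot be excluded, and under it the defect is one of wording only. This should be fixed, but it concerns one secondary endpoint and leaves the primary non-inferiority comparison untouched.

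**What to change.** State in SAP 2.3: for each subject, average the absolute value of profile minus audiogram over both ears and all tested frequencies from 500 to 6000 Hz; the endpoint is met if the upper limit of the two-sided 95% CI of the across-subject mean, computed from these subject-level values, is no more than 10 dB. Working at subject level respects the correlation between ears and frequencies within a person.

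Name the sample. Report by frequency the signed bias, the 95% limits of agreement and the share of thresholds within 10 dB. The 10 dB is the SAP's own figure; the sponsor should give its reason for it on the absolute scale. If any of these data have already been examined, date the change and report the result under both readings.

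The paired values are already planned, so the work is wording and a few lines of analysis. The real cost is a stricter criterion. At SD 10 dB (mean absolute error 8 dB) with an assumed 12 values per subject, it passes about 92% to 100% of the time for within-person correlation 0.1 to 0.5. With perfectly correlated errors that falls to about 80% (n=75) or 52% (n=37). At SD 8 dB it passes at least 98% in every case examined.
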